6.2 Secondary Endpoints

Secondary endpoints include preliminary examination of symptom change (EDE, ABOS) and rate of weight gain.

6.3 Statistical Methods

6.3.1 Baseline Data

Baseline and demographic characteristics will be summarized by standard descriptive summaries (e.g. means and standard deviations for continuous variables such as age and percentages for categorical variables such as gender).

6.3.2 Safety Analysis

All participants enrolled will be included in the safety analysis. Frequency of hospitalization and referral to a higher level of care will be summarized. Differences between those who need hospitalization and those who do not over the course of the study will be explored and reported.

6.4 Sample Size and Power

Power analysis Aim 1. In the initial phase of the proposed project (R61), our sample size estimation is based on a mixed MANCOVA design with two repeated measures from baseline to end-of-treatment (EOT; within subjects component) and three groups (CRT_P, CRT_A, and FBT; between subjects component). Based on a review of the literature, we are powering for a medium effect size. Our effect size estimate is Cohen's f statistic.⁹⁸ This effect size estimate is a ratio of variation explained to that unexplained by the model (treatment groups), and is expressed as

follows: $f = \sqrt{\frac{\eta^2}{(1-\eta^2)}}$, where $\eta^2 = \frac{\sigma_{model}^2}{\sigma_{Total}^2}$; proportion of variability due to the model.^{99,100}

Heuristics for small, medium, and large effect sizes are .1, .25, and .4, respectively. We selected an alpha of 0.15, given the nature of the study and the difficulty in recruiting participants from a low prevalence condition. Alpha of 0.15 is essential to provide adequate power for this study.⁹¹ As any analysis powered for a medium effect will also be powered for a large effect, we only highlight the expected medium effect. For all analyses, we specified an $\alpha=0.15$, two time points, and a correlation between measures of .3 (based on unpublished data). The anticipated N accounts for dropouts (i.e., number enrolled will be higher).

Power analysis Aim 2. Using Mplus 7.2,⁹⁴ we conducted a LGCM Monte Carlo simulation with 1000 replications^{94,101-103} to determine power to identify CRT_{P/A} dosage based on a half standard

deviation increase (rate of change; slope) from baseline (effect size) above FBT. With 15 participants in 3 groups across 5 time points, parameter and standard error bias were $\leq 5\%$, confidence interval coverage $\geq 90\%$, and power = 0.59.

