3.3 Study Duration, Enrollment and Number of Sites

3.3.1 Duration of Study Participation

Total study duration for each participant is approximately 12-14 months. Participants will have 6-12 months of active treatment. If there is a delay in treatment (brief hospitalization or cancelation of an appointment due to weather, illness, etc.) treatment duration may be slightly longer. It is anticipated that all treatment will be complete within 12-14 months of enrollment.

Adolescents and their families will be assessed at five time points:

- T₁: neuropsychological assessment, therapy session, questionnaires, Grocery store (parents), Buffet challenge (adolescent)
- T₂: therapy session, questionnaires
- T₃: neuropsychological assessment, questionnaires
- T₄: neuropsychological assessment, questionnaires, Grocery store (parents), Buffet challenge (adolescent)
- T₅: questionnaires, neuropsychological assessment, Grocery store (parents), Buffet challenge (adolescent)

- T₆: Medical chart review and questionnaires (to be completed online/ mailed to the family, this will take place 3 months post end of primary treatment intervention)
- T₇: Medical chart review and questionnaires (to be completed online/ mailed to the family, this will take place 6 months post end of primary treatment intervention)

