3.3.2 Total Number of Study Sites/Total Number of Subjects Projected

The study will only be conducted at Children's Hospital of Philadelphia.

It is expected that approximately 60 subjects will be enrolled to produce at least 45 evaluable subjects.

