6 STATISTICAL CONSIDERATIONS

6.1 Primary Endpoint

Aim 1: To identify whether or not it more impactful to add a parent or adolescent component of CRT to standard FBT. To assess if CRT engages the target, we will use mixed 3 (treatment) x 2 (time) Multivariate Analysis of Covariance (MANCOVA): one for adolescents, one for mothers, and one for fathers. The covariate for all analyses is total IQ on the WASI. Dependent variables are as follows: Trails Number-Letter Sequencing, Inhibition, Inhibition/Switching, Correct Response Shifting, Category Switching, or Description 1 or 2 and Shift on the BRIEF-2. We will follow these steps:

1. Conduct omnibus MANCOVA and evaluate significance. If not significant, stop and move to next analysis.
2. If the omnibus test is significant, we will conduct individual 2 (treatment) X 2 (time) Analysis of Covariance (ANCOVA) to determine which dependent variable had significant change, with IQ again as the covariate.
3. Each assessment of the target (DV) will be examined. Results will inform the Go/No-Go Decision as described in Table 6.

These three steps will be repeated for adolescents, mothers, and fathers. We will include all three groups in the initial MANCOVA and follow-up with planned comparisons (ANCOVA) of FBT vs the appropriate CRT condition. In all analyses, we will focus on the within and between-group effects, examining interaction effects are not necessary to evaluate the target. As we have chosen measures demonstrated to change with CRT,^{40,87-90} we will maintain $\alpha=0.15$ for each analysis.⁹¹ We do not expect adolescents whose parents receive CRT or parents whose adolescents receive CRT to demonstrate increases in flexibility. However, should the planned ANCOVAs not be significant, we will be able to explore other possible group differences. Additionally, we will explore the relationship between dependent variables via discriminant analysis. These additional methods to examine the data will not factor into the Go/No-Go decision, but will enhance the depth of our understanding of the data and contribute to our understanding of neurocognition in AN.

Aim 2: To determine the dose of CRT needed to lead to a medium effect size. Some research indicates that ≥ 8 sessions of CRT are necessary for improvement in cognitive flexibility with AN.⁹² It is unknown how many sessions will be needed for significant change in parents of

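### Aim 1 uses only baseline and end-of-treatment scores, leaves the T3 and T4 scores on the same outcomes unused, and does not say how a missing T5 score is handled

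*Combined protocol and SAP*

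**What the plan says.** Section 6.1 specifies a "mixed 3 (treatment) x 2 (time) Multivariate Analysis of Covariance (MANCOVA") for adolescents, mothers and fathers separately, with IQ as covariate. If that omnibus test is significant, two-group, two-time ANCOVAs follow. The dependent variables are "Trails Number-Letter Sequencing, Inhibition, Inhibition/Switching, Correct Response Shifting, Category Switching, or Description 1 or 2 and Shift on the BRIEF-2". Section 6.4 powers Aim 1 on "two repeated measures from baseline to end-of-treatment"; for every analysis "we specified an $\alpha=0.15$, two time points, and a correlation between measures of .3".

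The same measures are collected mid-treatment. Section 3.3.1 lists "T₃: neuropsychological assessment, questionnaires" and "T₄: neuropsychological assessment, questionnaires, Grocery store (parents), Buffet challenge (adolescent"). Table 1 and sections 4.2.3 and 4.2.4 agree, and Table 1 shows both D-KEFS and BRIEF-2 at these visits.

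Four other places bear on a missing T5 score:
- Section 3.3.2 enrols about 60 "to produce at least 45 evaluable subjects" and does not define the term.
- Section 4.8 asks withdrawing subjects for the questionnaire battery. If the family declines, the last visit supplies the final data point.
- Section 7.3.1 removes from analysis participants whose sessions had inadequate adherence ratings.
- Section 6 defines no Aim 1 analysis set and no missing-data method.

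**The concern.** The primary comparison rests on T5, yet the plan does not say what happens to a person without it. Two readings are open. The model in 6.1 suggests complete cases. Section 4.8 suggests single carry-forward, although its wording is about questionnaires and it arranges no early-termination D-KEFS testing. A complete-case analysis ignores a leaver's T3 and T4 scores. Carry-forward treats an earlier score as if it were the T5 score.

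Loss related to outcome is plausible. Section 4.6 removes adolescents referred to a higher level of care from trial treatment, and section 4.7 allows discontinuation for non-adherence or adverse events. Aim 1 results feed the Go/No-Go decision (6.1 step 3, section 10) at alpha 0.15, so a shift of a tenth of an SD caused by an unstated choice matters.

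**Working it through.** **Figures in the plan.** The implied loss is 1 − 45/60 = 25%, and 45/(1 − 0.25) = 60. This shows consistency only, because no dropout rate is stated. The readable text gives no Aim 1 power figure to reproduce.

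**Precision: inputs.** From the documents: 60 enrolled in three arms (20 per arm), 45 evaluable (15 per arm), baseline-T5 correlation .3. Assumed: all 25% lack T5; leavers are spread evenly before T3, T4 and T5, so 18.33 per arm have T3 and 16.67 have T4; .7 as an upper correlation; correlations either equal at all lags or decaying over sessions 0, 8, 11 and 15; covariance known; common baseline mean.

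**Formula.** Let v1, v13 and v134 be the variance of T5 given T1, given T1 and T3, and given T1, T3 and T4 (total variance 1). Per arm:
- T1 and T5 completers: v1/15
- All visits: v134/15 + (v13 − v134)/16.67 + (v1 − v13)/18.33

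| Correlation | v1 | v13 | v134 | Completers | All visits | Information gain |
|---|---|---|---|---|---|---|
| .3, equal | .910 | .8615 | .8313 | .06067 | .05988 | 1.3% |
| .3, decaying | .910 | .6749 | .4738 | .06067 | .05648 | 7.4% |
| .7, equal | .510 | .4235 | .3875 | .03400 | .03271 | 3.9% |
| .7, decaying | .510 | .2832 | .1732 | .03400 | .03052 | 11.4% |

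If all losses come after T4, the second line becomes v134/15 + (v1 − v134)/20. For .3 equal this is .8313/15 + .0788/20 = .05935, a gain of 2.2%. For .7 decaying it is .1732/15 + .3368/20 = .02839, a gain of 19.8%.

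Sessions become less frequent later in treatment (section 1.2.1). If decay runs over assumed weeks 0, 8, 14 and 26 instead, the two decaying gains in the table fall to 3.6% and 6.9%.

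**Against complete-case change scores.** Here arm baselines are estimated separately, and leavers have T3 and, for all or half of them, T4. The effective total is then about 49 to 53 instead of 45. Keeping leavers' baselines alone gives 46.8 to 49.3; T3 and T4 add about 1 to 4 more.

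**Bias.** Simulation with at least 200,000 persons per arm and scores oriented so that higher is better. Assumed: 30% of FBT leave, with odds 2.7 to 4 times higher per SD lower T4 score; 20% of CRT leave; leavers have T4 scores; FBT improves 0.3 SD; the true CRT effect is 0 or 0.5 SD.

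| Analysis | T4-dependent in FBT, random in CRT |
|---|---|
| Completers, change | 0 to −0.10 SD |
| Carry-forward | 0 to about +0.14 SD (+0.16 with no true effect) |
| All-visit model | under 0.01 SD |

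The zero for completers occurs when correlations are equal at all lags and the 0.10 when they decay over sessions. On the calendar scale at correlation .3, the 0.10 falls to about 0.02. If loss depends on T4 in both arms, the completer change contrast is off by about 0.03 SD or less.

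For scale, section 6.4 uses half an SD as its Aim 2 effect: 0.10/0.5 = 20% and 0.14/0.5 = 28%.

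**The case against.** A reader might infer that every family without T5 is discarded. The documents do not say so. Section 4.8 offers a carry-forward rule, BRIEF-2 can be obtained at early termination, and the unit of analysis is the person, since adolescents, mothers and fathers are analysed separately. What stands is that section 6 does not adopt the rule or any other.

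Nor do the documents show that 15 of 60 lack T5. Evaluable is undefined, and persons removed under 7.3.1 may have complete scores. The 25% is therefore an assumption at the high end.

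T3 and T4 are not the only data that could inform dropout. Weight is taken at treatment visits, a brief EDE is collected weekly, and several scales are given at T2. T3 and T4 are, however, the direct earlier measurements of the Aim 1 outcomes. Aim 2 does use mid-treatment data in a growth model fitted by maximum likelihood, but that does not repair the Aim 1 comparison.

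A larger bias, up to 0.19 SD, can be produced for a baseline-adjusted completer contrast. It does not apply here, because the planned covariate is IQ, not baseline score. The one-arm dropout scenario is an illustration with no support in the documents. The near-zero bias of the all-visit model follows from simulating dropout that depends only on an observed score.

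Finally, a T1-to-T5 change contrast is an arm-by-visit effect, and 6.1 says interactions are not needed to evaluate the target. That tension is real. The hypothesis in 2.1, however, is a greater increase than under FBT alone, which is a difference in change.

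**Conclusion.** The point holds in this form: Aim 1 leaves two collected waves of its own outcomes unused and states no rule for a missing T5 score, and the two rules that can be read into the text are both weaker than a likelihood analysis of all visits.

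The size is modest. The information gain is about 1-11% with evenly spread losses and up to about 20% if all losses follow T4. The bias is 0-0.10 SD for completers, or 0 to about +0.14 SD for carry-forward, when loss tracks T4 in one arm; it is about 0.03 SD or less for completers when loss tracks T4 in both arms. The two readings err in opposite directions in the one-arm case, so the choice between them should not be left open. Bias, more than precision, is the reason to change. All these figures rest on the assumed 25% loss, correlations and dropout patterns.

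**What to change.** For each Aim 1 outcome, separately for adolescents, mothers and fathers, make the planned FBT-versus-CRT comparison with a mixed model for repeated measures on T1, T3, T4 and T5: arm by visit, unstructured covariance, REML with small-sample degrees of freedom, and the IQ covariate. Include every randomised person with at least one score. Take the contrast in T1-to-T5 change; do not average visits.

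Do not let the complete-case two-time MANCOVA in step 1 gate this. Either run the planned contrasts regardless, or base the omnibus test on the same all-visit data.

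State that this replaces the carry-forward wording of 4.8 for Aim 1. Reconcile it with the undefined evaluable count in 3.3.2, the adherence exclusion in 7.3.1, and the statement in 6.1 that interactions are not needed. Keep the two-time analysis as a sensitivity analysis.

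The cost is SAP wording and slightly more analysis work. The model relies on data being missing at random and needs a 4 x 4 covariance matrix estimated from a small sample.

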7 STUDY MEDICATION (STUDY DEVICE OR OTHER STUDY INTERVENTION)

7.1 Description

All treatment will be delivered by a doctoral- or Master's-level psychologist. All therapists will be trained in FBT and CRT and will have their adherence to the manual supervised by the PI. These clinicians will be designated and added to section 1.02 of the eIRB once hired. Treatment will be delivered at the Robert's Center for Pediatric Research.

7.2 FBT

FBT was described in section 1.2.1. 15 sessions of FBT will be administered over the course of 6-12 months, with the option to participate in an additional 12 follow-up FBT sessions.

7.3 CRT

CRT was described in section 1.2.2. 15 sessions of CRT will be administered over the course of 6 months for families in CRT_A and CRT_P.

7.3.1 Treatment Compliance and Adherence

Treatment Fidelity. Sessions will be conducted by doctoral- or Master's-level therapists with training in FBT for AN. Prior to study start, therapists will attend a 3-day workshop with the PI. The first day reviews FBT; days 2-3 provide training in CRT. [name] will provide weekly supervision of FBT and CRT.

Treatment sessions will be videotaped and a random selection of 20% tapes per patient will be reviewed for adherence to FBT and CRT. FBT fidelity will be assessed using published methods,¹⁰⁴ CRT fidelity will be assessed by measures developed by the PI and used in a recent CRT pilot study. A trained master's level research assistant will score tapes for adherence and review weekly with [name]. In the event that a participant receives care that is a significant deviation from protocol (lack of adequate adherence ratings on more than 20% of sessions), this participant's data will be removed from analyses. If drift occurs, therapists will complete a refresher training session, the next three sessions will be reviewed and if improvement to criterion does not occur, the therapist will be withdrawn.

Missed sessions. Should a therapist miss a session (due to illness or vacation) the session will be rescheduled, the other therapist will see the family to ensure that a week is not missed, or the family will be asked to schedule two sessions the following week. Should the family need to cancel, all attempts will be made to reschedule within the week to ensure the family stays on schedule. If an appointment cannot be rescheduled within the week, the family will have two sessions scheduled the following week.

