1.2.2 Cognitive Remediation Therapy

CRT is an adjunctive intervention focusing on the development of meta-cognition – teaching individuals to think about how they think.⁴⁴ It involves presenting individuals with a variety of

tasks requiring increasingly complex mental abilities – these include geometric figures, illusions, reversing sequences of numbers and letters, completing sorting tasks wherein the rules change, and finding various routes on a map.⁴⁵ Most importantly, CRT focuses on process instead of outcome. That is, instead of focusing on whether or not a task was accurately completed, individuals in CRT are asked to think about how they solved a puzzle, reflect on their thought processes, and identify steps in problem solving. CRT has three goals:

1. Improve brain function by exercising and increasing connections in the brain
2. Encourage individuals to think about their thinking style
3. Encourage individuals and families to spend time away from thinking about the eating disorder.

CRT can be delivered in individual, family, and group formats.⁴⁶⁻⁴⁸ For this study, we will administer CRT to either adolescents or their parents. CRT will be delivered for 45-60 minutes prior to FBT sessions for a total of 15 sessions. Participants in CRT will be given weekly homework.

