3.1.3 Study Treatment Phase (start of the study intervention)

After the baseline assessment/intake, the family will be randomized to one of three conditions: Family Based Treatment (FBT), Parent Focused Cognitive Remediation Therapy + FBT (CRT_P), or Adolescent Focused Cognitive Remediation Therapy + FBT (CRT_A). Families will have 15 sessions of the assigned treatment and be assessed at 4 additional time points (baseline intake + 4 more is a total of 5 time points). For treatment, all standard clinical procedures will be followed.

In the event of an unforeseen circumstance whereby one's presence at CHOP puts the patient, family, and/or CHOP staff at risk, treatment sessions can be done remotely. All treatment sessions done remotely will take place on a CHOP-approved video conferencing app, such as Vidyo or Skype Business. If treatment sessions are done remotely, we may ask the family to weigh their child and share this weight with the study therapist. A note to file is being made for every treatment session that occurs remotely and will be reported to the IRB and DSMB in a yearly report.

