9.4.4 Risk-Benefit Assessment

Risks are minimal. All adolescents will receive family-based treatment – the most recommended treatment for adolescents with AN. Two groups will receive an additional session of CRT each week. Adolescents will be required to have medical care during the course of the study. If they are not improving, recommendations for a higher level of care will be given. The benefits of finding a way to improve outcomes out-weighs the minimal risk.

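### Randomised participants are dropped from the analyses on therapist-adherence ratings made after randomisation, no all-randomised set is stated for Aims 1 and 2, and the 20% trigger has no defined denominator

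*Combined protocol and SAP*

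**What the plan says.** Section 7.3.1 provides that "a random selection of 20% tapes per patient will be reviewed for adherence to FBT and CRT". FBT is scored with published methods and CRT with measures developed by the investigator. Where care departs significantly from protocol, the consequence and its threshold are given together: "lack of adequate adherence ratings on more than 20% of sessions), this participant's data will be removed from analyses". If a therapist drifts, there is a refresher session and the next three sessions are reviewed.

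Section 6.1 sets out the MANCOVA for Aim 1 and the growth model for Aim 2, and section 6.2 lists the secondary endpoints. Neither names an analysis population. The only statement covering everyone is in section 6.3.2: "All participants enrolled will be included in the safety analysis". Section 3.3.2 expects that "approximately 60 subjects will be enrolled to produce at least 45 evaluable subjects", without defining *evaluable*. Section 6.4 adds "The anticipated N accounts for dropouts (i.e., number enrolled will be higher", with no rate and no mention of removals for poor adherence. Section 4.8 says what serves as the last data point for families who withdraw. That is a missing-data rule, not an analysis set.

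On what counts as a session, sections 7.2 and 7.3 give 15 sessions of FBT and 15 of CRT. Section 1.2.2 says "CRT will be delivered for 45-60 minutes prior to FBT sessions for a total of 15 sessions", section 3.1.3 says "Families will have 15 sessions of the assigned treatment", and section 4.2.1 lists 15 treatment visits for every arm (1-8, 10-12, 14-17). Section 9.4.4, however, says "Two groups will receive an additional session of CRT each week".

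**The concern.** Aim 1 (section 2.1) is a randomised comparison of CRT with FBT alone, and section 6.1 says its results inform the Go/No-Go decision. Randomisation protects that comparison only while participants stay in the analysis regardless of what happens afterwards. Section 7.3.1 is the only stated rule on whose data are left out, and it acts on something observed during treatment. If poor ratings go with harder cases, the arms compared are no longer the arms randomised.

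The second difficulty is that the rule cannot be applied in only one way. It sets a limit on sessions, but ratings exist for only about a fifth of them. Two analysts could each follow the text faithfully and analyse different people.

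**Working it through.** **Inputs.** 20% of tapes rated per patient, a limit of more than 20% of sessions, and three reviews after drift (section 7.3.1); 15 FBT sessions (7.2); 15 CRT sessions in two arms (7.3). The plan prints no number of rated tapes, trigger count or expected number of removals, so there is no figure of its own to reproduce on this point. The Aim 2 power of 0.59 in section 6.4 plays no part here.

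**Tapes rated for a completer.** 0.20 × 15 = 3. If CRT and FBT give separate tapes, 0.20 × 30 = 6.

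**Reading A: the denominator is all sessions.** Exceeding 20% needs 4 inadequate of 15 (27%) or 7 of 30 (23%). The routine sample supplies at most 3/15 = 20% or 6/30 = 20%, neither above the limit. So routine review cannot remove a completer. If the three reviews after drift count for that participant, 3 + 3 = 6 tapes are rated and 4 of 15 becomes reachable. Non-completers differ through rounding: 2 tapes of 8 sessions, or 3 of 12 if rounded up, is 25%.

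**Reading B: the denominator is rated tapes.** With 3 rated, one inadequate tape is 1/3 = 33%, so one is enough. For K inadequate sessions of 15, P(removal) = 1 − C(15−K, 3)/C(15, 3), with C(15, 3) = 455. This uses only the protocol's own sampling.

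| K of 15 | True share | Over the 20% limit? | P(removal) |
|---|---|---|---|
| 1 | 7% | no | 1 − 364/455 = 0.20 |
| 2 | 13% | no | 1 − 286/455 = 0.37 |
| 3 | 20% | no | 1 − 220/455 = 0.52 |
| 4 | 27% | yes | 1 − 165/455 = 0.64 (kept: 0.36) |

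**Does reading B act alike in every arm?** Take one inadequate session in each set of 15 (7%). An FBT-only completer is removed with probability 0.20. For a CRT completer there are three possibilities:

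- One tape per visit, with 1 of 15 visits inadequate: 3 rated, trigger 1, probability 0.20, the same as FBT.
- Two tapes per visit, pooled: 6 of 30 rated; 1/6 = 17% is not enough and 2/6 = 33% is. P = C(28, 4)/C(30, 6) = 20,475/593,775 = 0.03.
- Two tapes per visit, FBT and CRT judged separately, with failure on either enough: 1 − (1 − 0.20)² = 0.36.

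The order is the same if each tape is instead assumed to fail independently at 2%, 5% or 10% (rates not in the documents). FBT alone, 1 − (1 − p)³: 0.06, 0.14, 0.27. Pooled, at least 2 of 6: 0.01, 0.03, 0.11. Separate, 1 − (1 − p)⁶: 0.11, 0.26, 0.47. Removal in the CRT arms can therefore be lower than, equal to or higher than in FBT, depending on a convention that the plan does not state.

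**The case against.** The best defence is context. This is a target-engagement phase, section 5.2 disclaims any efficacy evaluation, and the question is whether CRT can shift flexibility at all. Whether CRT works when delivered to standard is a fair question, and restricting to well-delivered cases is partly a choice of estimand. Weekly supervision and refresher training may keep failures rare. All of this stands, but it supports a labelled per-protocol analysis. It does not support making an ambiguous exclusion after randomisation the only stated rule.

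Four stronger readings are tempting, and the documents do not support them.

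- *The trigger is unworkable because only a fifth of tapes are rated.* It can be applied if rated tapes are the denominator, arguably the natural reading, since ratings exist only for those tapes. On the all-sessions reading it can be reached if reviews after drift count. The defect is an undefined and coarse denominator.
- *The rule biases the comparison in a known direction.* The contrast between arms reverses between pooled and separate judging. The 15 common visits in section 4.2.1 fit one tape per visit, where the trigger is the same in every arm.
- *Removals will cost power.* Section 3.3.2 allows 60 − 45 = 15 losses. It does not say whether fidelity removals fall inside that number, and no failure rate is given.
- *The safety analysis is compromised.* Section 6.3.2 is specific and can reasonably govern the general wording in section 7.3.1. One clarifying line is enough.

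It is also fair to say that analysing everyone with outcome data still depends on who completes assessment. The fix removes selection on fidelity; it does not supply missing outcomes.

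**Conclusion.** The point holds on two counts. First, section 7.3.1 selects randomised participants on therapist ratings made after randomisation, and nothing in sections 6.1 or 6.2 restores an all-randomised set for Aims 1 and 2. Second, the denominator, the tapes per CRT visit and the pooling of FBT and CRT ratings are not stated.

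The misclassification figures of 0.52 and 0.36 assume a completer with 15 tapes, 3 drawn at random, and rated tapes as the denominator; they need no assumed failure rate. Bias is zero if removal is unrelated to outcome, and no figure is put on it here. The effect on Go/No-Go cannot be checked, because Table 6 is not in the available text. This should be fixed because the rule is unsafe and ambiguous and the repair is cheap; a large distortion has not been shown.

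**What to change.** For Aims 1 and 2, state that all randomised participants with outcome data are analysed in their assigned arm, whatever their fidelity ratings, and define *evaluable* in section 3.3.2 to match. Keep the adherence exclusion only as a labelled per-protocol sensitivity analysis. For that analysis, state one denominator (rated tapes or all sessions), whether reviews after drift count, whether a CRT visit gives one tape or two, whether FBT and CRT ratings are pooled or judged separately, the number of inadequate tapes that triggers exclusion, and how non-completers are counted. Apply these identically in every arm. Add a line that the exclusion never applies to the safety analysis in section 6.3.2.

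The cost is wording in the protocol and SAP: no new data or visits, and no change to the planned MANCOVA or growth model. The downside is that poorly delivered cases may slightly dilute the effect, which the per-protocol analysis would show.
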